Comparing Autologous Blood, Corticosteroid, and Their Combined Injection for Treating Lateral Epicondylitis: A Randomized Clinical Trial

[name]

[contact] ORCID: [name]

**1. Istanbul Training and Research Hospital, Department of Orthopedics and Traumatology,
Istanbul, Turkey**

Corresponding author: [name] [name]

Address:

E-mail: **GSM:** +90

Compliance with the ethical standards

- Conflict of interest: Authors have no conflict of interest to declare.
- Funding: No funds have been received for this study.
- Ethical approval: The Institutional Review Board approved the study protocol (2023/137)
- Informed consent: Written informed consent was provided by the participants.
- Acknowledgements: None
- Data availability statement: Data are available from the authors upon reasonable request.
- Authors' contribution: Study conception and design: AC, Acquisition of data: AC, Analysis and interpretation of data: AC, Drafting of the manuscript: AC, Critical revision: AC, (Initials of authors' names)

Comparing Autologous Blood, Corticosteroid, and Their Combined Injection for Treating Lateral Epicondylitis: A Randomized Clinical Trial

Abstract

Objective: This study aimed to compare the efficacy of autologous blood (AB) and corticosteroid (CS) injections, as well as their combination, in treating lateral epicondylitis (LE).

Design: Randomized controlled trial

Methods: A total of 120 patients diagnosed with lateral epicondylitis were divided into three therapeutic injection groups. The AB group received a mixture of 1 ml of autologous venous blood and 2 ml of 2% prilocaine HCl (Priloc %2, Vem, Turkey). The CS group received a mixture of 1 ml of 40 mg methylprednisolone acetate (Prednol-L 40 mg, Mustafa Nevzat, Turkey) and 2 ml of 2% prilocaine HCl. The combined group received a mixture of 1 ml of autologous venous blood, 1 ml of 40 mg methylprednisolone acetate, and 1 ml of 2% prilocaine HCl. Follow-up assessments were conducted on days 15, 30, and 90.

Keywords: Lateral epicondylitis; Tennis elbow; autologous blood; corticosteroid

Level of evidence: Randomized clinical trial, Level 1 evidence

Abbreviations

AB: Autologous blood, **CS:** Corticosteroid, **LE:** Lateral epicondylitis, **PRTEE:** Patient-rated tennis elbow evaluation, **HGS:** Hand Grip Strength

1. Introduction

Lateral epicondylitis (LE) is a common musculoskeletal disorder affecting the extensor tendons of the forearm, manifesting as pain on the lateral side of the elbow and functional limitation during daily activities. Despite its name suggesting inflammation, histopathological examinations of the tendon reveal non-inflammatory angiofibroblastic tendinosis, accompanied by neovascularization, disorganized collagen, and mucoid degeneration [1, 2]. Since tendon degeneration is the underlying pathology, an effective therapeutic approach should reverse the degeneration to regeneration, ensuring symptom relief without recurrence.

Although many treatments exist, a consensus on the optimal single treatment for LE remains elusive. Traditionally, injections have served as a preliminary measure before resorting to surgical interventions, especially in resistant cases. However, an increasing number of alternative injections have been described in recent literature [3]. Newer injection therapies, such as autologous blood (AB) injections and platelet-rich plasma (PRP), have gained prominence and found favor among orthopedic surgeons. Multiple studies have attested to the safety and efficacy of AB and PRP injections as treatment modalities [4-7]. However, corticosteroid (CS) injections continue to be among the most commonly employed treatments for LE. A significant drawback of CS injections is their high recurrence rate. Patients typically experience a swift recovery immediately after injection, which endures for about a month. Unfortunately, this transient relief—often referred to as the 'honeymoon period'—is short-lived, leading to a recurrence of symptoms. Such a response pattern is well-documented in existing studies [8]. Conversely, AB injection therapy tends to proffer a gradual yet consistent reduction in symptoms, boasting a recurrence rate markedly lower than that of CS. It is postulated that AB addresses the intrinsic degeneration of the tendon, with its restorative process inherently spanning a more extended period [9-11].

We hypothesized that a combination of CS and AB injection might offer a superior treatment for LE. This combination may provide a faster resolution of symptoms due to the initial action of CS and provide a lower recurrence rate due to the regenerative action of AB. The purpose of this randomized clinical trial is to test three different types of injection for the treatment of LE: (1) AB, (2) CS, and (3) their combination (AB+CS).

2. Materials and methods

2.1. Patients and study design

A randomized clinical trial was carried out on eligible patients with a diagnosis of LE presented to our outpatient clinic. The diagnosis of LE was made with typical symptoms and physical examination findings, including pain and tenderness localized to the origin of forearm extensors and discomfort on the provoked wrist and middle finger extension. Patients whose complaints persisted for more than 3 months were evaluated for inclusion in the study.

Patients with a history of recent trauma, congenital or neuromuscular disease or abnormality of the upper limb, previous upper limb surgery, and history of rheumatic disease, history of cervical disc

pathology or carpal tunnel syndrome, systemic corticosteroid treatment, any previous local injection treatment, and finally patients with a history of previous allergic reaction towards local anesthetics and corticosteroids were all excluded from the study. All patients were over 18 years of age. The local ethical committee approved the study protocol (Approval number: 2023/137), and all patients gave their informed consent prior to their inclusion in the study. This prospective study was carried out following the ethical standards laid down in the 1964 Declaration of Helsinki and its later amendments.

2.2. Treatment groups and randomization

After taking informed consent, patients were randomly allocated into three treatment groups (AB versus CS versus their combination) with sealed envelopes prepared by a computer-based random number generator. A total of 120 envelopes were divided into three equal groups, 40 patients in each group. Patients in the AB Group received 1 ml of autologous venous blood mixed with 2 ml of 2% prilocaine HCl, patients in the CS Group received 1 ml of 40 mg methylprednisolone acetate mixed with 2 ml of 2% prilocaine HCl, and patients in the Combined Group (AB+CS) received 1 ml of autologous venous blood, 1 ml of 40 mg methylprednisolone acetate mixed with 1 ml of 2% prilocaine HCl. Each group received an equal amount of (3 ml) injected material. Venous blood was collected from the antecubital fossa of the ipsilateral extremity. The senior author performed all injections, and neither the physician nor the patient was blinded to the treatment modality. The injection was administered in aseptic conditions, and the needle was introduced over the maximal tenderness point; the content of the syringe was injected at once to prevent further bleeding. All patients were instructed to abstain from heavy work, and no additional therapy, including NSAIDs or physiotherapy, was prescribed.

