2.3. Follow-up and outcome measures

Functional outcomes were assessed with the patient-rated tennis elbow evaluation questionnaire (PRTEE). This outcome score consisted of 15 items related to three subscales, namely pain (5 questions), specific activities (6 questions), and daily activities (4 questions). The total score ranges between 0-100 points, 0 points designates the best functional outcome, whereas 100 points designates the worst functional outcome [12, 13]. To interpret PRTEE results, a minimum clinically important difference (MCID) value previously described by Poltawski et al. was used [14]. According to his study, a 37% decrease in PRTEE is considered a 'complete recovery' or clinically significant change. PRTEE was assessed before the injection (baseline values), on Day 15, Day 30, and Day 90, in the

same manner by the senior author. The same author performed follow-up and data collection. No patients received more than one injection in this clinical trial.

Hand grip strength (HGS) was measured with a digital hand dynamometer before and after injection in all patients. The senior author performed the measurements according to the American Society of Hand Therapists guidelines [15]. Since HGS varies according to factors such as height, weight, age, and gender, each patient's hand grip strength was calculated as a percentage increase from baseline.

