2.4. Sample size calculation

In our pursuit to determine the optimal sample size for our study on LE treatments utilizing PRTEE scores, we based our assumptions on several crucial parameters. We anticipated a 37% change in baseline PRTEE scores and considered a standard deviation (SD) of 10, drawing from previous studies. We adopted a conventional significance level (α) of 0.05 and aspired for a power of 0.90, applying the ANOVA testing methodology for three distinct treatment groups. Our computations indicated that to discern this 37% shift in PRTEE scores with the targeted power and significance level, a sample size of roughly 33 participants per group would be essential. Thus, given the three treatment groups in our research design, the aggregate sample size was estimated at 99 participants. However, taking into account a 20% dropout rate, the study included a total of 120 patients, with 40 patients in each group.

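### The PRTEE, the only outcome behind the sample size, is assessed by the unblinded author who gave every injection, and how it is administered is not stated

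*Combined protocol and SAP*

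**What the plan says.** Section 2.2 is open about the lack of blinding: "The senior author performed all injections, and neither the physician nor the patient was blinded to the treatment modality". Patients are allocated by sealed envelope after consent.

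Section 2.3 gives the visit schedule: "PRTEE was assessed before the injection (baseline values), on Day 15, Day 30, and Day 90". It describes the assessment as done in the "same manner by the senior author. The same author performed follow-up and data collection". Grip strength is in the same hands: "The senior author performed the measurements according to the American Society of Hand Therapists guidelines". The PRTEE is called a patient-rated questionnaire, but the section does not say whether the patient completes it alone or the author reads out the items and records the answers.

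Section 2.4 sets out "to determine the optimal sample size for our study on LE treatments utilizing PRTEE scores" and uses no other outcome for sizing. Neither these sections nor section 2.5 describes an independent assessor, a self-completion procedure or any other safeguard on data collection.

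**The concern.** One person knows the arm, gives the treatment, obtains the main outcome and records it. The introduction states the hypothesis that the combination may be superior, so this person also has an expectation about the result. If the author prompts patients or interprets their answers, and does so differently by arm, the difference goes straight into the PRTEE comparison. No analysis in section 2.5 could detect or remove it. Its direction is unknown and need not be the same at every visit.

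Baseline may be affected as well. It is fixed only as preceding the injection, which leaves open that it is taken after the envelope has been opened. Section 2.3 treats a 37% decrease in PRTEE as a clinically significant change, so an influenced baseline would alter that reading too.

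Patient unblinding is a separate source of bias. It may be hard to avoid, since only two of the three arms use the patient's blood. Assessor influence on a self-report form is avoidable.

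**Working it through.** **The passages together**

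| Question | What the plan gives | Section |
|---|---|---|
| Who injects? | The senior author, all patients | 2.2 |
| Is the injector blinded? Is the patient? | Neither | 2.2 |
| Who assesses the PRTEE and collects data? | The senior author | 2.3 |
| Who measures grip strength? | The senior author | 2.3 |
| PRTEE self-completed or by interview? | Not stated | 2.3 |
| Baseline before the envelope is opened? | Not stated; only before injection | 2.2, 2.3 |
| Outcome used for sizing | PRTEE only | 2.4 |

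The concern follows from these entries alone and disputes no figure in the plan. The arithmetic below only shows how sensitive the planned comparison is to a reporting shift.

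**Inputs.** From section 2.4: three groups, ANOVA, α = 0.05, SD 10 (taken as PRTEE points; the unit is not stated), 33 evaluable per arm and 40 enrolled per arm. The enrolled figure follows from 33 × 1.2 = 39.6, rounded up to 40. Assumed, with no source in the documents: a reporting shift of d points in one arm, no true effect, and an alternative SD of 20.

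**Formula.** With arm means (d, 0, 0), the sum of squared deviations from the grand mean is (2/3)d². The noncentrality parameter of the one-way F test is therefore

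λ = n × (2/3) × (d/SD)²

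The false-positive rate is the probability that a noncentral F with 2 and 3n − 3 degrees of freedom exceeds the 5% critical value. That value is 3.091 for n = 33 (2 and 96 df) and 3.074 for n = 40 (2 and 117 df).

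**Worked example.** For n = 33, d = 2, SD 10: λ = 33 × (2/3) × 0.04 = 0.88, giving 12.0%. For n = 40: λ = 40 × (2/3) × 0.04 = 1.067, giving 13.6%.

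| Assumed shift d | SD 10, n = 33 | SD 10, n = 40 | SD 20, n = 33 | SD 20, n = 40 |
|---|---|---|---|---|
| 0 | 5% | 5% | 5% | 5% |
| 2 | 12.0% | 13.6% | 6.6% | 7.0% |
| 3 | 21.8% | 25.8% | 8.8% | 9.7% |
| 4 | 36.1% | 43.0% | 12.0% | 13.6% |
| 5 | 53.1% | 62.1% | 16.3% | 19.0% |

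**Scale.** With 33 per arm, 90% power and SD 10, the design detects a 7.7-point difference of one arm from two equal arms. A 2-point shift is about a quarter of that (2/7.7 = 0.26).

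**The case against.** The strongest reply is that the instrument is by name patient-rated. On the ordinary reading the patient supplies the ratings, and the author's part may be no more than handing out and collecting the form. The harm is then conditional, and what the documents show is an unstated mode of administration. This stands in part: nothing shows that prompting took place, and self-rating would reduce assessor influence. It would not remove it if the form is completed in front of the injector, and the plan does not exclude an interview. The statement that assessment was uniform does not settle the matter, because an assessor who knows the arm can follow one procedure and still influence answers by arm.

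Second, the unblinded patient is the rater, so the fix leaves what may be the larger bias in place, and the assessor's share is unknown. That is correct, and it limits what the change can achieve. It is not a reason to leave the avoidable part.

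Third, the numerical shifts are assumed, would have the same effect whatever their cause, and relate to a single ANOVA. Section 2.5 switches to Kruskal-Wallis for non-normal data, and there are three follow-up visits with none named as primary. This also stands. The figures run from 6.6% to 62.1% across the assumed 2- to 5-point shifts and are not a risk estimate.

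Fourth, section 2.5 names no responder analysis, so the baseline effect on the 37% threshold concerns interpretation and not a specified test. That is so.

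Finally, the text is in the past tense and the visits may be over. In that case only the reporting part of the fix applies.

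**Conclusion.** The concern holds as a weakness of design, not a contradiction: the lack of blinding is disclosed. As written, the plan puts its only sizing outcome in the hands of the unblinded injector at all four time points, without stating the mode of administration, the timing of baseline relative to allocation, or any safeguard.

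The actual bias cannot be estimated from the documents, and neither can the part due to the assessor as against the unblinded patients. The sensitivity figures assume a shift in one arm only, no true effect and an omnibus ANOVA at one visit. They show that the comparison tolerates little at the planned SD of 10, where 2 points on a 100-point scale more than doubles the nominal 5%, and considerably more if the SD is nearer 20. The change should be made; confidence is medium, because the harm depends on how the form was in fact used.

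**What to change.** In section 2.3:

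- State how the PRTEE is administered.
- Have patients complete it on paper, unassisted: at baseline after consent but before the allocation envelope is opened, and on Days 15, 30 and 90 before the consultation with the senior author.
- Score it from the sheet by the fixed scoring key. The author checks only that no item is blank.
- Report as limitations that patients were unblinded and that the same unblinded author measured grip strength.

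If the visits are already complete, state the mode that was used and report the single unblinded assessor as a limitation for both outcomes.

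The cost is a printed form, a change in visit order and occasional missed items. No second assessor is needed; the text should say how forms are handed out and returned. The change does not remove the expectation bias of unblinded patients, does not protect the grip-strength measurement, and leaves the sample size as it is.

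### Patients are unmasked for a patient-rated outcome, although AB versus AB+CS could be patient-masked with no added procedure

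*Combined protocol and SAP*

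**What the plan says.** On masking, section 2.2 (Treatment groups and randomization) states: "The senior author performed all injections, and neither the physician nor the patient was blinded to the treatment modality". It gives no reason, and no section describes a screen, a covered syringe, a sham draw or independent collection of the questionnaire.

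On the outcome, section 2.3 states: "Functional outcomes were assessed with the patient-rated tennis elbow evaluation questionnaire (PRTEE". The instrument runs from 0 (best) to 100 (worst) and is taken at baseline and on Days 15, 30 and 90. The injector also runs follow-up: "The same author performed follow-up and data collection".

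On what is injected, section 2.2 gives three recipes:
- AB: "Patients in the AB Group received 1 ml of autologous venous blood mixed with 2 ml of 2% prilocaine HCl".
- CS: "patients in the CS Group received 1 ml of 40 mg methylprednisolone acetate mixed with 2 ml of 2% prilocaine HCl".
- AB+CS: "received 1 ml of autologous venous blood, 1 ml of 40 mg methylprednisolone acetate mixed with 1 ml of 2% prilocaine HCl".

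It adds: "Each group received an equal amount of (3 ml) injected material". Section 2.3 says that nobody had more than one injection.

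On the aim, the Introduction states: "We hypothesized that a combination of CS and AB injection might offer a superior treatment for LE". It expects quicker relief from the steroid component and less recurrence from the blood component.

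**The concern.** When the patient supplies the score, an unmasked patient is an unmasked assessor, whoever hands over the form. Masking the staff who collect the questionnaire would not by itself remove this.

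The hypothesis has two limbs. Quicker relief from adding steroid to blood is tested by AB+CS versus AB. Less recurrence from adding blood to steroid is tested by AB+CS versus CS. On the first limb, a PRTEE difference could reflect the steroid, or what patients expect of a two-component injection, and the open design cannot separate them. For this contrast the plan's own recipes make patient masking possible at little cost, so the exposure is avoidable at least in part.

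**Working it through.** **1. Can AB and AB+CS be made to look alike to the patient?** From sections 2.2 and 2.3:

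| Feature | AB | AB+CS | CS |
|---|---|---|---|
| Blood in the mixture | 1 ml | 1 ml | none |
| Methylprednisolone | none | 1 ml (40 mg) | 1 ml (40 mg) |
| 2% prilocaine | 2 ml | 1 ml | 2 ml |
| Total volume | 3 ml | 3 ml | 3 ml |
| Injections | 1 | 1 | 1 |

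AB and AB+CS both need venous blood, one injection and 3 ml. They differ in one millilitre, steroid in one arm and prilocaine in the other. Masking the patient between them adds no venepuncture, injection or volume. The CS mixture contains no blood, so masking against CS would need a further step such as a sham draw.

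**2. The plan's own figures.** Section 2.4 gives 33 per group (α 0.05, power 0.90, three-group ANOVA, SD 10), raised to 40. The 33 cannot be rebuilt, because the 37% change is relative to a baseline PRTEE that is not stated. Solving backwards, 33 per group at 90% power needs Cohen's f = 0.363. At SD 10 that is a largest difference between means of 0.363 × 10 × 3/√2 = 7.7 points (one arm differs from two equal arms) or 0.363 × 10 × √6 = 8.9 points (evenly spaced means). This gives a scale for the shifts below. The masking point does not depend on it.

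**3. What a reporting shift would do.** The documents give no figure for expectation bias, so the shift b is an assumption. Suppose there is no true difference and AB+CS patients report b points better than AB patients. For a two-sided 5% t test:

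- SE = SD × √(2/n); noncentrality = b/SE; df = 2n − 2.
- The false-positive rate is the probability that a noncentral t exceeds the critical value in either tail.

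| SD | n per arm | SE | Noncentrality, b = 2 / 3 / 5 | False-positive rate, b = 2 / 3 / 5 |
|---|---|---|---|---|
| 10 | 40 | 2.236 | 0.894 / 1.342 / 2.236 | 0.143 / 0.263 / 0.598 |
| 10 | 33 | 2.462 | 0.812 / 1.219 / 2.031 | 0.126 / 0.225 / 0.516 |
| 15 | 40 | 3.354 | 0.596 / 0.894 / 1.491 | 0.091 / 0.143 / 0.313 |
| 20 | 40 | 4.472 | 0.447 / 0.671 / 1.118 | 0.073 / 0.102 / 0.197 |

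SD 10 and the two sample sizes come from section 2.4. SDs of 15 and 20 are assumptions, to show the range. With b = 0 every row returns 0.05. The rates are the same if the shift favours AB, because the test is two-sided; only the direction of the false finding changes.

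**4. The planned test.** Section 2.5 names ANOVA or Kruskal-Wallis across three groups and no pairwise test. With AB and CS equal and only AB+CS shifted, f = (b/SD) × √2/3. At SD 10 and 40 per arm, f = 0.094, 0.141 and 0.236 for b = 2, 3 and 5, and the ANOVA rejects in 13.6%, 25.8% and 62.1% of trials. The pairwise picture therefore carries over to the omnibus test.

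**The case against.** The strongest reply is that the mask would leak.

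- **Anaesthetic volume.** AB has 2 ml of prilocaine and AB+CS has 1 ml, which could give the patient a cue.
- **Early response.** The Introduction itself contrasts a rapid response to steroid with a slower one to blood, so patients might guess their arm by Day 15 or Day 30.
- **The injector.** The person who knows the allocation sees the patient at every visit, so the mask rests on that person's discretion.

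All three stand. They make the mask imperfect without making it worthless, and they are reasons to record patients' guesses.

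A second reply is that only one limb of the hypothesis is protected, and that the three-group test would then mix masked and open arms. That also stands, and the report should say so.

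Some stronger readings are tempting but not supported:

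- A reader might infer that the bias is known to favour the combination. The documents give neither its direction nor its size. The Introduction also speaks well of autologous blood and lists recurrence as a drawback of steroid, so expectations could run either way.
- A reader might treat AB+CS versus AB as the central comparison. No primary contrast is named, and the hypothesis rests equally on AB+CS versus CS.
- A reader might conclude that the authors judged masking impossible in every arm. Section 2.2 reports that nobody was blinded and does not say why.

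**Conclusion.** The point holds within limits. Leaving patients unmasked on a patient-rated outcome opens every PRTEE contrast to expectation bias, and nothing elsewhere in the document offsets this. For AB+CS versus AB alone, patients could have been masked with no added procedure. This is a worthwhile, low-cost improvement; it is not evidence that any result is false.

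The sizes are illustrative. At SD 10 and 40 per arm, assumed shifts of 2 to 5 points take a nominal 5% error rate to between 14% and 60%; at SD 20 the range is 7% to 20%. The 60% should not be read as the trial's actual error rate, since it needs both a 5-point shift and an SD of 10. Feasibility rests on the recipes in section 2.2 and on keeping the syringe contents from view, because the document does not describe what the mixtures look like.

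**What to change.** **If patients remain to be treated**

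- In section 2.2, state that patients allocated to AB or AB+CS are not told which of the two they received until the Day 90 PRTEE is complete, unless disclosure is needed for their care. The mixture is drawn up out of the patient's sight and the syringe is covered.
- In section 2.3, state that patients complete the PRTEE themselves without discussing allocation. At each follow-up visit, after the PRTEE, record which injection they think they had.
- Describe the trial as patient-masked for AB+CS versus AB only. State that contrasts with CS alone, and the three-group test that includes CS, remain open-label and carry possible expectation bias.

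The cost is protocol and consent wording, a syringe cover and one extra question per visit. No extra visit or procedure is needed, and no sample-size figure changes. What remains is an unmasked injector who collects outcomes, and possible cues from the prilocaine volume or an early steroid response. Having someone else collect the PRTEE would reduce the first, but that is a separate change that needs staff.

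**If patients have already been treated**, as the past tense throughout may suggest, masking can no longer be applied. The report should then say that patients were unmasked and that all PRTEE contrasts carry possible expectation bias of unknown size and direction.
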